7.3 SUBJECTS

The study cohort will be formed based on the following entry criteria.

Inclusion Criteria:

- 1. At least one prescription for Tio+Olo or a LABA/LAMA/ICS combination between 1 January 2013 and 31 March 2019.
 - a. For Tio+Olo users, the first dispensing of Tio+Olo will be defined as the index date.
 - b. LABA/LAMA/ICS use can occur either in free or fixed combinations. The first date when all three medications are used based on either concurrent or overlapping dispensings in the pharmacy claims data will be defined as the index date.
- 2. At least one diagnosis of COPD at any time prior to the index date.
- 3. At least one year of continuous medical and pharmacy health plan eligibility prior to the index date will be required to allow a baseline period for the covariates and identification of new use of the study drugs.

Exclusion Criteria:

- 1. To increase the likelihood of a true diagnosis of COPD, we will exclude:
 - a. All patients less than 40 years of age on the index date, and
 - b. All patients with a diagnosis of asthma in the year prior to the index date
- 2. To limit the population to those without severe lung compromise outside of COPD, we will exclude individuals with lung cancer, interstitial lung disease, or lung transplant identified at any time prior to the index date
- 3. To restrict the cohort to new users of Tio+Olo or LABA/ICS, we will exclude any individual with use of either Tio+Olo, LABA/ICS, or LABA/LAMA/ICS combination therapy in free or fixed form for at least one year prior to the index date.

Outpatient laboratory data is available for a subset of patients. Some analyses will be further restricted to the subset of the population with at least one laboratory result showing circulating eosinophil levels within six months before the index date.

Individuals in the study cohort will be followed from the index date until the earliest of the date of a switch in treatment, addition of ICS for the Tio+Olo group, discontinuation of

COPD treatment, the end of the study period, or the end of continuous health plan eligibility. Main analyses will be further limited to the first year after cohort entry, with sensitivity analyses considering all available data.

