7.4 VARIABLES

7.4.1 **Exposures**

The exposure measures are based on pharmacy dispensings of the study medications, namely Tio+Olo and LABA/LAMA/ICS combination therapy. As described in the data analysis section, the as-treated analysis, which is the main analysis, will consider continuing exposure of the initial treatment of Tio+Olo or LABA/LAMA/ICS within the treated groups defined by the days supply recorded at the time of pharmacy dispensing, allowing for a gap between dispensings of up to 15 days. This gap is allowed in consideration of plausible delays in obtaining medication refills and continued use beyond the days supplied where medication has been missed due to imperfect adherence, and will be varied in sensitivity analyses (see Section 7.9.2). Codes used to identify study medications are included in Annex 3.1.

The treatment segment ends at the earliest of the following events:

- 1. Fifteen days after the end of the observed days supply for the medication received on the index date without a subsequent dispensing of COPD medication (i.e., discontinuation)
- 2. Initiation of triple therapy (i.e., addition of ICS to Tio+Olo or a LAMA to LABA/ICS (i.e., treatment escalation, applies to Tio+Olo only)
- 3. Any other change in use of study medication by active ingredient, inclusive of a change to a different combination therapy, change from a fixed form to a free form combination therapy, or a change from combination therapy to monotherapy (i.e., switch)

Changes in dose for medications started on the index date will not impact the end of the treatment segment. Codes used to identify study medications are included in Annex 3.1.

7.4.2 **Outcome(s)**

7.4.2.1 **Primary outcome(S)**

The primary outcome event for effectiveness is the first COPD exacerbation to occur after cohort entry. The event is defined as follows:

- Severe exacerbation: •
 - Hospitalization with a principal discharge diagnosis of COPD.
 - Moderate exacerbation:
 - An ED visit with a discharge diagnosis of COPD and/or
 - Dispensing of an antibiotic and an oral corticosteroid on the same day

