Time to the first COPD exacerbation will be measured from cohort entry until the occurrence of a hospitalization for COPD (severe exacerbation) or ED visit for COPD with the prescription of an antibiotic and/or an oral corticosteroid on the same day (moderate exacerbation). Severe and moderate exacerbations will be considered as a composite for main analyses. Sensitivity analyses will stratify by exacerbation severity.

Although there is precedent for defining moderate exacerbation based on use of antibiotics for a respiratory infection without requiring concomitant oral corticosteroids, we have chosen

a more restrictive definition of exacerbation. Because diagnoses listed on outpatient claims often correspond to a patient's past medical history in addition to acute problems, we expect limited ability to capture the indication for which antibiotics are prescribed. As such, including antibiotics alone as a case definition for exacerbation would introduce potentially substantial misclassification of outcome where antibiotics were truly given for non-respiratory infections. Given that our analyses will yield estimates on a ratio measure, non-differentially reduced sensitivity is a less important threat to validity than reduction of outcome specificity, which produces an expectation of bias towards the null hypothesis. In order to test our assumptions that the sensitivity of our outcome definition is not differential between the Tio+Olo and LABA/ICS groups, we would produce counts of patients with antibiotics alone during follow-up, and determine whether the proportion of potential exacerbations that we excluded through this design decision is comparable across groups.

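### Section 7.4.2.1 words the ED component of the primary outcome in two conflicting ways and states the COPD diagnosis position in neither

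*Combined protocol and SAP*

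**What the plan says.** Section 7.4.2.1 of the combined protocol and SAP gives the primary event as a list.

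- Severe: "Hospitalization with a principal discharge diagnosis of COPD".
- Moderate: "An ED visit with a discharge diagnosis of COPD and/or" a second item, "Dispensing of an antibiotic and an oral corticosteroid on the same day".

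The paragraph after the list, which defines time to first exacerbation, words the moderate event differently: "ED visit for COPD with the prescription of an antibiotic and/or an oral corticosteroid on the same day (moderate exacerbation".

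Four other places bear on how these are read.

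- Section 7.3, inclusion criterion 2, requires "At least one diagnosis of COPD at any time prior to the index date".
- Annex 3.2 gives one COPD code list for outcomes. It includes general codes such as 496 and J44.9 and is not confined to acute exacerbation.
- Section 7.4.2.1 explains why antibiotics alone do not count as an event: "Because diagnoses listed on outpatient claims often correspond to a patient's past medical history in addition to acute problems", the indication for an antibiotic is hard to establish. It adds that "non-differentially reduced sensitivity is a less important threat to validity than reduction of outcome specificity, which produces an expectation of bias towards the null hypothesis".
- Section 7.4.3 lists ED visits among the moderate exacerbations at baseline, again with no diagnosis position.

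**The concern.** The primary event cannot be programmed from this section without choosing between two rules. Under the list, an ED visit is enough if COPD appears among its discharge diagnoses. Under the paragraph, the visit must be for COPD and be accompanied by an antibiotic or an oral corticosteroid. The two rules give different event counts and different first-event dates.

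Diagnosis position matters because COPD does not discriminate within this cohort. Every patient has it on record, and a general COPD code may be carried onto a claim for an unrelated problem. The word 'principal' guards against this in the hospitalization limb. Nothing equivalent appears in either ED wording.

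Two results are at stake. The first is the primary hazard ratio, which non-specific events would be expected to dilute. The second is the exacerbation-history stratification, which relies on ED events at baseline.

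**Working it through.** **1. The two wordings side by side**

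| Feature | List in 7.4.2.1 | Paragraph after the list |
|---|---|---|
| Does an ED visit qualify without a drug? | Yes, under the 'or' | No |
| Drug requirement | Separate item: antibiotic and oral corticosteroid together | Antibiotic and/or oral corticosteroid, with the ED visit |
| COPD diagnosis position for ED | Not stated | Not stated (the visit is 'for COPD') |
| COPD position for hospitalization | Principal | Not repeated |

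**2. What each wording lets in**

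Consider a cohort member seen in the ED for another cause, with 496 or J44.9 as a secondary code.

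- List: the visit meets the literal wording.
- Paragraph: without a same-day antibiotic or oral corticosteroid it does not count. If an antibiotic is given for a non-respiratory infection, it could count, provided 'for COPD' is programmed as a COPD code in any listed position.

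**3. Size of the dilution**

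Let a and b be the true-event and false-event hazards in the reference arm, with b the same in the other arm. Let f = b/(a+b) be the false share of all reference-arm composite events. Then

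observed HR = (a × HR + b)/(a + b) = (1 − f) × HR + f.

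The only effect size in the documents is 0.85, in Section 7.7, taken there from an earlier CPRD analysis. It serves here as an illustration.

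- f = 10%: 0.90 × 0.85 + 0.10 = 0.865
- f = 20%: 0.80 × 0.85 + 0.20 = 0.880
- f = 30%: 0.70 × 0.85 + 0.30 = 0.895

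The share f is assumed. It refers to the whole composite, which includes hospitalizations and, on the list wording, drug dispensings. It therefore cannot exceed the ED share of events, which the documents also do not give.

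**4. Power**

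Section 7.7 cites over 90% power for 0.85 with 2,000 patients per cohort. This cannot be reproduced, because no event rate or alpha is stated. With two-sided 0.05 assumed and 1:1 groups, Schoenfeld's formula gives

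events = 4 × (1.960 + 1.282)² / (ln 0.85)² = 1,592,

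or 1,592/4,000 = 39.8% of patients with an event. The cited figure is attainable but not verifiable.

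| f | Observed HR | Power at 1,592 recorded events | Power if false events are added to 1,592 true events |
|---|---|---|---|
| 0 | 0.850 | 90.0% | 90.0% |
| 10% | 0.865 | 82.5% | 86.5% |
| 20% | 0.880 | 72.3% | 82.0% |
| 30% | 0.895 | 60.0% | 76.3% |

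These rows describe the 1:1 benchmark, not this study. At the preliminary counts in Section 7.7 (5,469 and 42,227, an 11.5% allocation to Tio+Olo), 90% power needs 3,919 events, or 3,919/47,696 = 8.2% of patients. In the overall cohort the bias in the estimate is therefore likely to matter more than the loss of power.

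**The case against.** The strongest reply is that the paragraph after the list already narrows the event: an ED visit for COPD with a same-day prescription is not an ED visit with COPD somewhere on the claim. This stands in part. A reader might infer that the protocol accepts COPD in any position, so that any ED visit for a fall or chest pain is recorded as an exacerbation. The documents do not say so. 'Any position' is an inference from silence and from the contrast with the hospitalization limb, and under the paragraph wording such visits would not count without a qualifying prescription. What remains is that the paragraph names no position either, lets an antibiotic alone suffice, and conflicts with the list.

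A reader might also infer that the protocol contradicts its own specificity argument. That argument is about the indication for antibiotics on outpatient claims. Applying it to ED discharge diagnoses is a reasonable extension, not a literal contradiction.

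The planned separate analyses of moderate and severe exacerbations help, because the severe analysis rests on hospitalizations and excludes ED visits. The main composite is still affected. The planned count of patients with antibiotics alone does not separate ED events by diagnosis position.

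Confounding through general ED use is not shown either. The propensity score includes the Charlson index, several comorbidities and data-derived variables, though residual confounding could remain. At baseline, the high-history stratum in Section 7.9.1 needs one hospitalization or two outpatient events, so a single incidental ED visit moves nobody who lacks another qualifying event.

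**Conclusion.** The point holds as an unresolved definition of the primary event, and it should be corrected. Section 7.4.2.1 gives two incompatible ED rules and no ED diagnosis position, in a cohort where a COPD code by itself says little about why a patient attended. ED visits with COPD as a comorbidity can enter the composite, readily on the list wording and more narrowly on the paragraph wording. The expected effect is dilution: 0.85 would be seen as 0.865 to 0.895 if 10% to 30% of reference-arm composite events were non-specific. This rests on an assumed share, an equal false-event hazard in both arms, and an effect size borrowed from another analysis. The documents do not show how large the misclassification would be, or that it would differ between arms.

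**What to change.** 1. Replace the two wordings in Section 7.4.2.1 with one ED definition. It should say whether an ED visit qualifies alone or only with a same-day antibiotic and/or oral corticosteroid, and whether a dispensing of both drugs qualifies without an ED visit.
2. Require COPD as the principal (first-listed) ED diagnosis, matching the hospitalization limb.
3. Apply the same rule to baseline ED exacerbations in Section 7.4.3 and in the history strata of Section 7.9.1.
4. Report the primary analysis with any-position ED visits as a sensitivity analysis, so that the effect of position is visible.

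This needs a few lines of text and one further run on existing claims. The downside is fewer events and some true exacerbations missed where COPD was coded second. If that loss is non-differential, it is the kind of error the protocol already ranks as less harmful than lost specificity; the any-position run would help show whether the choice matters.

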7.4.3 Covariates

Patient characteristics at baseline will be assessed for Tio+Olo and LABA/LAMA/ICS user overall and stratified by history of exacerbation, circulating eosinophils, subgroups defined by both exacerbation and eosinophil levels.

We will identify and describe the following demographic characteristics as of the index date:

- Sex
- Age (years, as both a categorical and a continuous variable)
- Calendar year of cohort entry

Proprietary confidential information © 2019 Boehringer Ingelheim International GmbH or one or more of its affiliated companies

- Season of index date (winter, spring, summer, fall)
- US census region of residence
- Insurance type (e.g., Commercial, Medicare)

Additional characteristics will be defined during the 12-month pre-index baseline period:

- Number of previous COPD treatments
- Specific previous COPD treatments
 - LAMA monotherapy
 - LABA monotherapy
 - ICS monotherapy
 - LAMA/ICS combination therapy
 - LABA/ICS combination therapy
- Previous acute COPD exacerbation (measured both overall and in the 30 days prior to cohort entry), categorized as 0, 1, or 2+.
 - All exacerbations (Moderate+Severe)
 - ED visits or dispensings of inhaled corticosteroids/antibiotics (Moderate)
 - Hospitalizations (Severe)
- Use of other respiratory drugs in the 12-month pre-index period:
 - Short-acting beta-agonists
 - Anticholinergics
 - Methylxanthines
 - Muscarinic antagonists
 - Short-acting muscarinic antagonists
- Use of antibiotics for a respiratory condition (e.g., azithromycin)

Chronic comorbidities will be defined using diagnoses identified during all available data prior to the index date, and will include:

- Cardiovascular disease
- Charlson comorbidity index
- Diabetes
- Thyroid disease
- Renal failure
- Autoimmune disease
- Pneumonia
- Obesity*
- Alcohol use disorder*
- Tobacco use or cessation counselling*
- Cancer (excluding basal cell carcinoma)
- * We anticipate limited capture of lifestyle variables known to be risk factors and potential confounders, including obesity, smoking status and excessive alcohol consumption. Although we will describe them as identified in the HIRD, bias analyses to examine the extent to which residual confounding may impact results are also planned.

Additionally to the covariates defined above, we will use the high-dimensional approach to identify variables entering a time-conditional propensity score.

Boehringer Ingelheim	

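### If the stand-alone pharmacy rule applies, a same-day refill of long-term oral corticosteroid and antibiotic counts as a first exacerbation; two wordings in section 7.4.2.1 disagree on this

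*Combined protocol and SAP*

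**What the plan says.** Section 7.4.2.1 sets the endpoint: "The primary outcome event for effectiveness is the first COPD exacerbation to occur after cohort entry". Its bulleted definition makes a moderate exacerbation either an ED visit with a COPD diagnosis and/or "Dispensing of an antibiotic and an oral corticosteroid on the same day". The second part needs no diagnosis or visit.

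The time-to-event sentence that follows words the moderate event differently: "ED visit for COPD with the prescription of an antibiotic and/or an oral corticosteroid on the same day". There, the drugs qualify an ED visit and do not form an event alone.

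The rationale then explains why an oral corticosteroid is required alongside the antibiotic: "including antibiotics alone as a case definition for exacerbation would introduce potentially substantial misclassification of outcome". It ranks the two kinds of error: "non-differentially reduced sensitivity is a less important threat to validity than reduction of outcome specificity". The one planned check of the definition is "we would produce counts of patients with antibiotics alone during follow-up".

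Section 7.3 does not exclude long-term users of oral corticosteroids or antibiotics. Section 7.4.3 lists baseline respiratory antibiotic use, autoimmune disease and exacerbation history as covariates. It lists no oral corticosteroid covariate, and its baseline moderate-exacerbation item names inhaled, not oral, corticosteroids. A high-dimensional propensity score is planned in addition (sections 7.4.3 and 7.9.1).

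**The concern.** The oral corticosteroid requirement is the plan's safeguard for specificity. It works when the pair of fills marks a new acute course. It fails for a patient already taking both drugs long term, because a joint refill then meets the rule with no acute event behind it. As only the first event counts, that refill ends the patient's contribution to the primary analysis.

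Equal shares of such events in both arms pull the hazard ratio towards 1, the consequence the plan itself describes: "reduction of outcome specificity, which produces an expectation of bias towards the null hypothesis". Unequal shares that survive weighting could move it in either direction. The antibiotic-alone count cannot detect this, because it looks for events missed, not for events wrongly counted.

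**Working it through.** **1. Does the rule count a refill?**

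- Bulleted definition in 7.4.2.1: yes. There is no days-supply limit, no washout and no diagnosis requirement.
- Time-to-event sentence in 7.4.2.1: no. An ED visit is required.
- Supporting text: the rationale for pairing the drugs fits the bulleted definition. So do the outpatient exacerbations used for the history strata in 7.4.3 and 7.9.1.

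The bulleted reading is the more likely one, but the text does not settle it.

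**2. The plan's own benchmark.** Section 7.7 cites a CPRD analysis with 2,000 patients per cohort, hazard ratio 0.85 and over 90% power. No event proportion is given, so the power can be neither reproduced nor refuted. With two-sided alpha 0.05 (assumed), Schoenfeld's formula gives

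events = 4 × (1.960 + 1.282)² / (ln 0.85)² ≈ 1,592, and 1,592 / 4,000 ≈ 40%.

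I use 40% as the upper end of the assumed risk. It applies here only if that setting carries over.

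**3. Equal false events in both arms.** Let r be the true risk in the reference arm over follow-up, and p the share of each arm that scores a false event. Neither is in the documents. With a true ratio of 0.85,

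observed ratio = [0.85·r·(1 − p) + p] / [r·(1 − p) + p]

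| r | p = 1% | p = 2% |
|---|---|---|
| 10% | 0.09415 / 0.1090 = 0.864 | 0.1033 / 0.1180 = 0.875 |
| 25% | 0.2204 / 0.2575 = 0.856 | 0.2283 / 0.2650 = 0.861 |
| 40% | 0.3466 / 0.4060 = 0.854 | 0.3532 / 0.4120 = 0.857 |

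This is a ratio of risks. A Cox score calculation over one year, with false events spread over days 1-30, agrees: at 20% risk, 0.85 becomes 0.857 (p = 1%) or 0.864 (p = 2%). At 40% risk it becomes 0.854 or 0.857.

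Neither calculation models as-treated censoring after a 15-day gap. If follow-up averaged 90 days (assumed), annual risks of 20% and 40% become 1 − 0.80^0.25 = 5.4% and 1 − 0.60^0.25 = 12.0%. With p = 2% the ratio is then 0.89 or 0.87, provided the refill precedes censoring.

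**4. Unequal false events, true ratio 1.** With shares p1 (triple therapy) and p0 (Tio+Olo) remaining after weighting,

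observed ratio, triple vs Tio+Olo = [r·(1 − p1) + p1] / [r·(1 − p0) + p0]

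For p1 = 3% and p0 = 1.5%:
- r = 10%: 0.1270 / 0.1135 = 1.12
- r = 25%: 0.2725 / 0.26125 = 1.04
- r = 40%: 0.4180 / 0.4090 = 1.02

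The Cox calculation with 2% triple and 1% Tio+Olo gives 1 / 0.954 = 1.05 at 20% risk and 1 / 0.976 = 1.02 at 40%.

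**5. Is such a difference plausible?** The only related figure is the high-history group in section 7.7:
- Tio+Olo: (226 + 105 + 537) / 5,469 = 868 / 5,469 = 15.9%
- Triple: (1,888 + 707 + 4,822) / 42,227 = 7,417 / 42,227 = 17.6%

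The whole group differs by 1.7 points before any adjustment. A residual gap of 1.5 points from the small subset of dual long-term users is not supported by anything in the plan.

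**The case against.** The strongest reply has four parts.

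- **The ED-visit sentence closes the gap.** It does if that version is programmed. But the bulleted text is the formal definition, and the rationale and outpatient strata fit it.
- **Existing controls limit the harm.** Long-term dual users would probably have several joint fills at baseline. If baseline outpatient events use the same rule, these patients fall into the high-history group, which is both a covariate and a stratum. Baseline antibiotic use, autoimmune disease and the high-dimensional score may help balance them, and a severe-only analysis that a refill cannot trigger is planned. This stands as mitigation. It does not remove the false events from the primary composite, and balance still leaves attenuation. The inhaled-corticosteroid wording at baseline also leaves it unclear whether the same rule applies.
- **The affected group may be tiny.** A false event needs long-term use of both drugs, same-day collection, and a refill before censoring. No document gives these frequencies. This stands.
- **The qualifying antibiotics are inferred.** The only antibiotic list shown, in Annex 3.3, is a covariate list. It includes azithromycin and trimethoprim-sulfamethoxazole, but the Annex 3.2 outcome table as available shows no antibiotic list. This also stands.

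A reader might infer that long-term users as a class score a false event soon after entry, or that the primary hazard ratio is biased against triple therapy. The documents support neither. The first depends on which wording is programmed and on same-day collection. The second needs a difference between arms that persists after weighting, for which there is no evidence.

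**Conclusion.** The concern holds, conditionally. Under the bulleted definition, a joint refill with no acute event counts towards the primary outcome, and no planned check would reveal it. Under the ED-visit sentence it does not count. The contradiction between them is certain; the refill problem depends on how it is resolved.

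The likely effect is modest attenuation: 0.85 reads about 0.85-0.88 if 1-2% of each arm score a false event and true risk is 10-40%. It would be somewhat more if as-treated follow-up is short. All these inputs are assumptions. Bias away from a true null, of the order of 1.02 to 1.12 in the scenarios shown, arises only if false-event shares still differ after weighting. The matter deserves correction because the plan itself treats loss of specificity as the greater threat and because the remedy is cheap.

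**What to change.** 1. Reconcile the bulleted definition and the time-to-event sentence in section 7.4.2.1, stating whether a dual fill without an ED visit is an event.
2. If the stand-alone pharmacy rule is kept, add baseline oral corticosteroid use (including continuous use) and continuous antibiotic use to the pre-specified propensity score covariates in section 7.4.3.
3. Add a sensitivity analysis of the primary outcome. Either exclude patients with continuous baseline supply of both drugs, or count the dual fill only when days supply and prior fills show a new course. State whether prior supply of one drug or of both disqualifies a fill, and apply the same rule to baseline outpatient events. The documents give no basis for a particular cut-off, so the study team should choose and justify it before analysis.

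The cost is a few sentences and minor programming on pharmacy claims the study already uses. The downside is that the sensitivity analysis misses some true exacerbations in long-term users. That is a loss of sensitivity, which the plan ranks as less serious than a loss of specificity.

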objectives:	with Tio+Olo in comparison to patients treated with ICS/LABA/LAMA. All analyses will be repeated in sub-groups of patients under high- or low risk of exacerbation based on (1) previous history of exacerbations in the year preceding cohort entry (with exacerbation history defined as either 1+ hospitalization or 2+ exacerbations in emergency department or outpatients settings [R05-1384]), and (2) circulating eosinophils (cut-off B-Eos 300 cells/uL [P18-09975]) Both overall and among those without a history of exacerbation. The primary objective is to compare the effectiveness of maintenance therapy initiation with the combination treatment Tiotropium and Olodaterol (Tio+Olo) compared with any LABA/LAMA/ICS combination in COPD as		
	The secondary objecti therapy initiation with LABA/LAMA/ICS co pneumonia. Additionally, we will a LABA/LAMA/ICS in cost overall and by car	ve is to assess the association be the combination treatment (Tio ombination in COPD and time to assess differences between Tio+ healthcare utilization and all-ca re setting.	etween maintenance +Olo vs any community acquired Olo vs any use and COPD-specific
Study design:	A incident new-user c via fine stratification	cohort design will be used, with and reweighting of time-condition	confounding controlled onal propensity scores

c30699487-01

IT			1
Name of company:			Boehringer
Boehringer Ingelheim			Ingelheim
Name of product: Spiol	to		_
Name of active ingredie	nt:		
Tiotropium bromide +	Olodaterol		
	1		
Protocol date:	Study number:	Version/Revision:	Version/Revision date:
12 December 2019	1237-0094	1.0	NA
© 2019 Boehringer Ingel This document may not - ir	Proprietary heim International GmbH n full or in part - be passed on, 1	confidential information I or one or more of its affiliated compreproduced, published or otherwise used wit	oanies. All rights reserved. hout prior written permission

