Protocol for non-interventional studies based on existing data	
BI Study Number 1237-0094	

Proprietary confidential information © 2019 Boehringer Ingelheim International GmbH or one or more of its affiliated companies

Sub-populations will include patients with high or low circulating eosinophils (B-Eos 300 cells/uL [P18-09975] as identified based on the laboratory result value that is closest but prior to the index date (within 6 months). Additional stratification will include previous history of exacerbations in the year preceding cohort entry (with exacerbation history defined as either 1 + hospitalization or 2 + exacerbations in emergency department or outpatients settings), and among those without a history of exacerbation at baseline, based on circulating eosinophil results as noted above. However, number of patients with baseline exacerbations and data available on B-Eos is very low (see section 7.7) and therefore analysis would not be meaningful and will not be performed.

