Stratified analyses will use the same approach. Because not all individuals will have available laboratory result data available, fine stratification and reweighting by propensity score will be repeated within the subset of the cohort with available results to create weighted populations suitable for these stratified analyses. Potential effect-modification by B-Eosinophils and/or exacerbation history will be studied by comparing models with and without interaction terms and through qualitative consideration of differences in stratum-specific estimates.

The analysis of the risk of pneumonia will also use a time-dependent Cox proportional hazard regression model with an as-treated approach, similar to that of the primary analysis.

In addition, we will repeat the primary effectiveness analysis on the time to exacerbation separately for moderate and severe exacerbations.

In terms of healthcare utilization, we will present continuous and categorical variables using standard descriptive statistics to describe total visits and total costs related to inpatient, outpatient, office visit, and emergency care as well as total pharmacy dispensings, distinct medications used, and pharmacy costs. Utilization and costs will be stratified to facilitate comparison between Tio+Olo and LABA/ICS, and presented by individual setting and as a composite. All-cause and COPD-specific data will be shown.

Proprietary confidential information © 2019 Boehringer Ingelheim International GmbH or one or more of its affiliated companies

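### Section 7.4.2.1 gives two different rules for a moderate exacerbation, a component of the primary composite; the baseline wording and the pneumonia code lists also need aligning

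*Combined protocol and SAP*

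**What the plan says.** Section 7.4.2.1 introduces the primary outcome with "The event is defined as follows". Its moderate limb has two bullets. The first is "An ED visit with a discharge diagnosis of COPD and/or" and the second is "Dispensing of an antibiotic and an oral corticosteroid on the same day". Either bullet is enough.

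The next paragraph says how time to first exacerbation is measured. There the moderate event is an "ED visit for COPD with the prescription of an antibiotic and/or an oral corticosteroid on the same day (moderate exacerbation". Severe and moderate events form one composite in the main analysis.

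The rationale that follows concerns outpatient claims and explains why both drugs are required. It argues that "including antibiotics alone as a case definition for exacerbation would introduce potentially substantial misclassification of outcome".

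Other sections rely on the same concept:

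- **Abstract and 7.4.3.** The high-risk history subgroup is "either 1+ hospitalization or 2+ exacerbations in emergency department or outpatients settings" in the abstract, and 7.4.3 likewise refers to "exacerbations in emergency department or outpatients settings".
- **7.4.3, baseline covariates.** Moderate events in the prior year are described by ED visits or dispensings of inhaled (not oral) corticosteroids and antibiotics, joined by a slash, with no same-day condition.
- **7.9.1.** The plan states that "we will repeat the primary effectiveness analysis on the time to exacerbation separately for moderate and severe exacerbations".

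For the secondary outcome, 7.4.2.2 and Annex 3.2 each give a list of pneumonia codes.

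**The concern.** The two statements in 7.4.2.1 swap the connectives. The definition joins the ED visit and the drugs by or, and requires both drugs. The time-to-event sentence joins them by and, and accepts either drug. A programmer who follows the sentence builds a different primary endpoint from one who follows the bullets. No text available to this review says which governs. The amendments section records none. Annex 3.4 is in the table of contents but was not in the text available here.

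The stakes are these:

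- The primary composite could have fewer or later first events than the definition gives.
- In the moderate-only repeat, the disputed rule is the entire endpoint.
- An antibiotic-plus-steroid event outside the ED could count towards a patient's exacerbation history but not as an outcome.
- The planned check counts patients with antibiotics alone during follow-up, so it would show neither kind of event lost between the two rules.
- The baseline wording describes a propensity-score covariate. Taken literally, it could count maintenance inhaled-steroid fills as exacerbations.

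**Working it through.** The plan gives no figure on this point to reproduce. The check compares rules and lists.

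**1. The two rules in 7.4.2.1.** Let E be an ED visit for COPD, A an antibiotic and O an oral corticosteroid, all on the same day. I treat prescription and dispensing as the same thing, because the data are pharmacy claims, and I take both descriptions of the ED visit to mean the same claim.

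- Definition: E or (A and O)
- Time-to-event sentence: E and (A or O)

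| Same-day pattern | Definition | Sentence |
|---|---|---|
| none | no | no |
| A only | no | no |
| O only | no | no |
| A + O, no ED visit | **yes** | **no** |
| E only | **yes** | **no** |
| E + A | yes | yes |
| E + O | yes | yes |
| E + A + O | yes | yes |

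The definition counts 5 of 8 patterns and the sentence 3 of 8: two lost, none gained. Every day that qualifies under the sentence also qualifies under the definition. A patient's first event under the sentence is therefore on the same day, later, or absent. COPD hospitalizations count under both rules. These are patterns, not frequencies.

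**2. An alternative reading.** Parsed less naturally as (E and A) or O, the sentence still disagrees with the definition in 2 of 8 patterns: it loses E only and gains O only. No reading tried makes the two agree.

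**3. Baseline moderate events (7.4.3).** Suppose the inhaled steroid is a slip for oral. If the slash means or, the rule is E or A or O. That counts 7 of 8 patterns, adding A only and O only to the definition. Counting A only contradicts the rationale in 7.4.2.1. If the slash means both drugs on one day, the rule counts 5 of 8 and matches the definition.

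The preliminary counts in 7.7 for the high-history stratum are:

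- Tio+Olo: 226 + 105 + 537 = 868; 868 / 5,469 = 15.9%
- Triple therapy: 1,888 + 707 + 4,822 = 7,417; 7,417 / 42,227 = 17.6%

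These shares do not suggest that inhaled-steroid fills were counted as exacerbations.

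**4. Pneumonia codes.** As extracted, Annex 3.2 has 36 ICD-9 and 34 ICD-10 entries, 70 in all. Outside the 7.4.2.2 list are 480, 480.1, 480.2, 480.3, 480.8, 480.9 and 997.31 (7 ICD-9), and J95.4 and J95.89 (2 ICD-10): 7 + 2 = 9 of 70. These entries are present in the annex, so loss in reading the PDF cannot explain them.

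In the other direction, 487.0, 507.x, 510.0, 510.9, 511.0, 513.0, 514.x, 517.1, 519.8, 530.84, J22, J85.0 and J86 appear in 7.4.2.2 but not in the annex as extracted. That direction is weaker evidence, because table rows may have been lost.

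**The case against.** The strongest reply is that the bullets are labelled as the definition, so a careful programmer would follow them and the later sentence is loose paraphrase. All harm is conditional on the sentence being coded. That limits the likely damage, but the sentence states how the primary time variable is measured, so it can be programmed as it stands.

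Second, the direction of the difference depends on how the sentence is parsed. This stands as a caveat: the strict-subset result holds on the natural reading, while the alternative gains one pattern and loses one. Neither restores agreement.

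Third, some of the supporting text is weaker than it looks. Section 7.9.1 splits history only into inpatient and outpatient events, and outpatient may include ED visits there. Only the abstract and 7.4.3 name the two settings separately, and none of these places says that an outpatient event means antibiotic plus oral steroid. The clash with the rationale is also partial, because an ED visit with an antibiotic is not antibiotics alone. These points are fair and do not touch the main conflict.

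Fourth, the baseline wording is probably a slip, and pneumonia concerns a secondary outcome. Both are graded lower here for that reason.

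Finally, the history subgroup has a further mismatch. Section 6 splits at 0-1 versus 2 or more exacerbations, with no hospitalization criterion, whereas the abstract, 7.4.3 and 7.9.1 use one hospitalization or two other events. That is correct and should be settled in the same edit.

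**Conclusion.** The concern holds. Section 7.4.2.1 contains two rules for a moderate exacerbation that cannot both operate, and the discordant text is the time-to-event sentence. On the natural reading it drops two of the five patterns that the definition counts and adds none. This must be fixed, because it decides what the primary composite and the moderate-only repeat measure.

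The documents give no frequency for the affected patterns and no expected event proportion, so neither the number of events lost nor any effect on power can be stated.

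The baseline wording in 7.4.3 is a linked repair; nothing shows that it was applied literally. The pneumonia mismatch is real and of lower grade. If the ICD-9 and ICD-10 content does not match, capture could shift at the October 2015 coding change noted in 7.5. That is only a possibility, and adjustment for calendar year and the time-conditional score would offset part of it.

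**What to change.** - **7.4.2.1:** reword the time-to-event sentence so that it refers to the bulleted definition and does not restate it.
- **7.4.3:** describe baseline moderate events by the same rule, with the oral corticosteroid, both drugs and the same-day condition explicit.
- **Abstract, Section 6, 7.4.3 and 7.9.1:** use one exacerbation-history cut-off, and say what an outpatient event is.
- **7.4.2.2 and Annex 3.2:** keep one pneumonia code list, checked for matching ICD-9 and ICD-10 content.

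All of this should be settled before analysis. The cost is wording and one reconciled code list, with no new data. Section 4 dates the start of extraction and coding to August 2019 and preliminary results to 19 December 2019, a week after the protocol date. If code already follows a different rule, some reprogramming and rerunning would be needed as well.
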